## 7.3 Dose modifications

KN046 will be withheld for  $\geq$  Grade 3 drug-related toxicity, including laboratory abnormalities with the exception of laboratory abnormalities that are not clinically significant or that do not meet the criteria of adverse event, and severe or life-threatening AEs (i.e. anemia grade 3, lymphocytopenia grade 3-4, hypercholesterolemia grade 3-4, hypertriglyceridemia grade 3-4).

If a dose of KN046 is withheld due to toxicity, subjects may resume dosing with KN046 when toxicity has improved to  $\leq$  Grade 1.

In case toxicity does not resolve to Grade 0-1 within 12 weeks after last infusion, trial treatment will be discontinued. With the agreement between investigator and Sponsor Medical Monitor, subjects with a laboratory adverse event at Grade 2 after 12 weeks may continue treatment only if asymptomatic and controlled, for example, hypothyroidism or Type 1 diabetes controlled by replacement treatments.

Subjects who require corticosteroids to manage drug-related adverse events must be at an equivalent dose of  $\leq 10$  mg per day of prednisone to resume dosing with KN046. In case of an inability to reduce the corticosteroid dose for managing a drug-related adverse event to the equivalent of  $\leq 10$  mg prednisone per day within 12 weeks of last KN046 dose, patient will go off treatment.

For a subject who experiences a recurrence of the same serious adverse event at the same grade or greater after rechallenge of KN046, study medication will be discontinued.

In addition, if any of below drug-related adverse events occur, KN046 treatment will be permanently discontinued:

- $\geq$  Grade 3 immune related pneumonitis;
- Recurrence of  $\geq$  Grade 2 immune related pneumonitis lasting  $\geq$  4 weeks after appropriate medical interventions;
- $\geq$  Grade 2 immune related CNS toxicities lasting  $\geq$  4 weeks after appropriate medical interventions;
- $\geq$  Grade 3 immune related colitis;
- $\geq$  Grade 3 uveitis or optic neuritis;
- $\geq$  Grade 3 immune related hepatitis with ALT/AST  $> 8 \times$  ULN OR TBIL  $> 3 \times$  ULN;
- $\geq$  Grade 3 immune related nephritis or renal dysfunction.
- $\geq$  Grade 2 myocarditis
- $\geq$  Grade 2 myositis

**Table 7-1** *Guideline on KN046 dose modification*

Toxicity	Grade	Withheld treatment	Resume treatment	Dose / schedule for resuming treatment	Discontinuation of treatment
Hematological toxicity	1, 2	No	Not applicable	Not applicable	Not applicable

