	3 (except for isolate event of grade 3 neutropenia)	Yes			

Toxicity	Grade	Withheld treatment	Resume treatment	Dose / schedule for resuming treatment	Discontinuation of treatment
	4	Yes	Toxicity resolves to $\leq$ Grade 1 or baseline within 12 weeks of last KN046 dose	Resume at planned dose and increase the dose interval by 1 week at each occurrence	Permanent discontinuation if toxicity does not resolve to $\leq$ Grade 1 or baseline within 12 weeks of last KN046 infusion
Non-hematological toxicity with the exception for alopecia of any Grade and Grade 2 fatigue which will be treated as Grade 1 adverse reaction (with the exception of those reported in 7.3)	1	No	Not applicable	Not applicable	Not applicable
	2	Yes	Toxicity resolves to $\leq$ Grade 1 or baseline within 4 weeks of last KN046 dose	Resume at planned dose and dose interval	Permanent discontinuation if toxicity does not resolve to $\leq$ Grade 1 or baseline within 12 weeks of last KN046 infusion
			Toxicity resolves to $\leq$ Grade 1 or baseline beyond 4 weeks and within 12 weeks of last KN046 dose	Resume at planned dose and increase the dose interval by 1 week at each occurrence	
	3, 4	Yes	Toxicity resolves to $\leq$ Grade 1 or baseline within 12 weeks of last KN046 dose	Resume at planned dose and increase the dose interval by 1 week at each occurrence	Permanent discontinuation if toxicity does not resolve to $\leq$ Grade 1 or baseline within 12 weeks of last KN046 infusion; Permanent discontinuation should also be considered for any life-threatening or severe adverse reactions

Note: if increased Grade 3 or 4 CPK occurs, myocardial enzymes (CPK, CK, Tn1, TnT) should also be measured. KN046 will be permanently discontinued in case of elevation on treatment-related myocardial enzymes
					

Infusion related reactions, hypersensitivity reactions, and immune related adverse event should be handled according to the guidelines provided in Sections 7.5.1 and Appendix A, respectively.

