**16. Appendix A: Guidelines on the management of immune related adverse events**

Only the general principles of treatment for relatively common immune-related adverse events are listed below. Other immune-related toxicities, including rare but severe immune-related toxicity treatments (such as immune-related ocular toxicity and central nervous system toxicity) can be found in ESMO (31) and NCCN (32). Subjects who have been treated for more than 3 weeks with steroids recommend the use of drugs such as sulfamethoxazole/trimethoprim to prevent opportunistic infections such as pneumocystis.

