**Table 06-1 Management of immune related pneumonitis**

CTCAE v5.0 Grade	KN046 Dosing Management	Action and Guidelines	Diagnostic Consideration
Grade 1 Asymptomatic. Radiographic changes only presenting as ground glass change, non-specific interstitial pneumonia	
 
Consider delay KN046 treatment
 
	
 
Monitor symptoms and signs every 2~3 days
 
Radiologic findings should be followed on serial imaging studies at least every 3 weeks
 
Consider pulmonary consultation. Perform bronchoscopy if clinically indicated
 
	All attempts should be made to rule out other causes such as metastatic disease, bacterial (eg, Legionella, Mycoplasma) or viral infection
Grade 2 Mild/moderate new symptoms of dyspnea, cough, chest pain	
 
Withhold KN046
 
Treatment with KN046 may be resumed if the event improves to <math>\leq</math>Grade 1 within 12 weeks and corticosteroids have been reduced to the equivalent of methylprednisolone 10 mg/day orally or less
 
Discontinue KN046 if upon rechallenge the patient develops a second episode of <math>\geq</math>Grade 2 pneumonia
 
Discontinue KN046 if Grade 2 pneumonia lasting for <math>\geq</math>4 weeks despite appropriate medical intervention
 
	
 
Rule out other causes such as infectious diseases
 
Consider pulmonary function tests
 
Consider pulmonary consultation. Perform bronchoscopy and biopsy/bronchoalveolar lavage (BAL) if clinically indicated
 
Start empirical antibiotics treatment if suspicion of infection (fever, CRP increased, neutrophil counts increased)
 
Consider hospitalization and monitor signs and symptoms every day
 
If no evidence of infection or no improvement in signs and symptoms with antibiotics after 48 hours, add in prednisolone 1 mg/kg/day (or equivalent) orally with prolonged
 
	

CTCAE v5.0 Grade	KN046 Management	Dosing	Action and Guidelines	Diagnostic Consideration
			taper lasting for at least 4 weeks	

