Grade 1 < 4 liquid stools per day over baseline		
 
• No change in KN046 dose
 
	
 
• For diarrhea, treat symptomatically (loperamide, oral hydration, electrolyte substitution, ADA colitis diet and avoid high fiber high lactose diet)
 
• Grade 1 diarrhea that persist for > 1 week should be treated with the addition of oral diphenoxylate hydrochloride and atropine sulfate four times daily and budesonide 9 mg daily
 
• Grade 1 diarrhea that persist for > 2 weeks should consider to add treatment with prednisolone 0.5~1 mg/kg (non-enteric coated)
 
• If diarrhea persists, endoscopy is recommended
 
	All attempts should be made to rule out other causes such as metastatic disease, bacterial or parasitic infection, viral gastroenteritis, or the first manifestation of an inflammatory bowel disease by examination for stool leukocytes, stool cultures, and a Clostridium difficile titer
Grade 2 4~6 liquid stools per day over baseline, or abdominal pain, or blood in stool or nausea or nocturnal episodes		
 
• Withhold KN046 till ≤ Grade 1
 
	
 
• Consultation with gastroenterologist and endoscopy is recommended to confirm or rule out colitis for Grade 2 diarrhea that persists > 1 week or Grade 1~2
 
	

CTCAE v5.0 Grade	KN046 Management	Dosing	Action and Guidelines	Diagnostic Consideration
			
diarrhea with rectal bleeding
 
 
Grade 2 diarrhea should be treated with the addition of oral diphenoxylate hydrochloride and atropine sulfate four times daily and budesonide 9 mg daily
 
Grade 2 diarrhea that persists > 1 week or Grade 2 diarrhea with diffuse ulceration and bleeding seen on endoscopy is recommended to add oral prednisolone 0.5~1 mg/kg (or equivalent) with prolonged taper lasting for at least 4 weeks prednisolone. Diffuse ulceration and bleeding seen on endoscopy represents an increased risk for the development of bowel perforation and indicates longer taper of steroid
 
	

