Grade 3-4 ≥7 liquid stools per day or life-threatening		
 
Withhold KN046 
 
KN046 will be permanently discontinued if ≥Grade 3 colitis is confirmed
 
Discontinue KN046 if unable to reduce corticosteroid dose to < 10 mg per day prednisone or equivalent within 12 weeks of toxicity
 
 
 
	
 
Require hospitalization
 
Endoscopy is recommended to confirm or rule out colitis
 
Grade 3-4 colitis 
 
Systemic corticosteroids should be initiated at a dose of 1~2 mg/kg/day of prednisone or equivalent. When symptoms improve to Grade 1 or less, corticosteroid taper should be started and continued over at least 4 weeks
 
 
 
Grade 3-4 diarrhea
 
	

CTCAE v5.0 Grade	KN046 Management	Dosing	Action and Guidelines	Diagnostic Consideration
			
 
Rule out bowel perforation. Imaging with plain films or computed tomography (CT) can be useful
 
Consider consultation with gastroenterologist and confirmation biopsy with endoscopy
 
Treat with intravenous (IV) steroids (methylprednisolone 125 mg) followed by high-dose oral steroids (prednisone 1~2 mg/kg once per day or equivalent). When symptoms improve to Grade 1 or less, steroid taper should be started and continued over no less than 4 weeks. Taper over 6~8 weeks in patients with diffuse and severe ulceration and/or bleeding
 
If IV steroids followed by high-dose oral steroids does not reduce initial symptoms within 48~72 hours, consider treatment with infliximab upon symptom relief and initiate a prolonged steroid taper over 6~8 weeks. If symptoms worsen during steroid reduction, initiate a retapering of steroids starting at a higher dose of
 
	

CTCAE v5.0 Grade	KN046 Management	Dosing	Action and Guidelines	Diagnostic Consideration
			
80 or 100 mg followed by a more prolonged taper with or without administration of infliximab. Caution: infliximab is contraindicated in patients with bowel perforation or sepsis
 

• If symptoms persist despite the above treatment, a surgical consult should be obtained

	

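### The Grade 2 pneumonitis row of Appendix A permits KN046 to restart at a steroid dose above the limit in section 7.3

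*Combined protocol and SAP*

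**What the plan says.** Section 7.3 sets a general rule for steroid-treated toxicity: "Subjects who require corticosteroids to manage drug-related adverse events must be at an equivalent dose of" no more than 10 mg prednisone per day to resume. If the dose cannot be brought down to the equivalent of at most 10 "mg prednisone per day within 12 weeks of last KN046 dose, patient will go off treatment". The rule covers drug-related events without exempting immune-related ones, and the list of permanent-discontinuation events that follows it names immune-related pneumonitis and colitis.

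Below Table 7-1, the same section directs that infusion reactions, hypersensitivity and "immune related adverse event should be handled according to the guidelines provided in Sections 7.5.1 and Appendix A, respectively".

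Two Appendix A rows carry their own steroid limit:

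- **Grade 2 pneumonitis (Table 06-1).** KN046 may restart if the event improves to Grade 1 or less within 12 weeks and "corticosteroids have been reduced to the equivalent of methylprednisolone 10 mg/day orally or less".
- **Grade 3-4 colitis/diarrhea (Table 0-2).** "Discontinue KN046 if unable to reduce corticosteroid dose to" below "10 mg per day prednisone or equivalent within 12 weeks of toxicity". The same cell stops KN046 permanently if Grade 3 or higher colitis is confirmed.

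The appendix describes its own scope modestly: "Only the general principles of treatment for relatively common immune-related adverse events are listed below". No sentence in either place says whether the 7.3 steroid limit still applies when Appendix A is being followed.

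**The concern.** A physician managing Grade 2 pneumonitis is sent from section 7.3 to Appendix A and finds a restart dose there. It is stated in a different steroid from the one in 7.3. If methylprednisolone is the more potent drug milligram for milligram, the appendix dose is the looser one. The row then permits what 7.3 rules out.

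At stake is a restart threshold after lung toxicity for an agent that blocks both PD-L1 and CTLA-4. Two treating physicians at this single center, or one physician reading different pages, could reach different decisions on the same patient, and each could point to protocol text in support.

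**Working it through.** No figure in the plan needs reproducing. The check compares the texts and adds some simple arithmetic.

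**1. Dose gap in the pneumonitis row.** Inputs: 10 mg/day prednisone (section 7.3); 10 mg/day methylprednisolone (Table 06-1); potency factor f, in mg prednisone per mg methylprednisolone. The documents give no f, so it is assumed.

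| f (assumed) | Appendix limit as prednisone, 10 × f | Excess over 7.3 | 7.3 limit as methylprednisolone, 10 / f |
|---|---|---|---|
| 1.0 | 10.0 mg | 0 | 10.0 mg |
| 1.2 | 12.0 mg | 2.0 mg | 8.33 mg |
| 1.25 | 12.5 mg | 2.5 mg | 8.0 mg |

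The appendix is looser for any f above 1. The gap closes only at f = 1.

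**2. Can a patient fall in the gap?** The pneumonitis row also stops KN046 if the Grade 2 event lasts 4 weeks or more despite treatment, so the event must resolve sooner. Illustration, in days after the last KN046 dose:

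- Onset on day 7 and Grade 1 on day 28. Duration is 28 − 7 = 21 days, under the 28-day stop rule.
- Day 28 is within 12 weeks (84 days).
- On day 35 the patient is on methylprednisolone 10 mg/day.

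Table 06-1 permits a restart on day 35. Section 7.3 does not until the dose falls to about 8.0 to 8.3 mg methylprednisolone.

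**3. Can Appendix A simply replace the 7.3 limit?** Seven rows shown both hold KN046 and provide for systemic steroids. Two state a milligram limit: Grade 2 pneumonitis and Grade 3-4 colitis/diarrhea. Four state none: Grade 2 diarrhea, Grade 2 hepatitis, Grade 3 rash and Grade 2 nephritis. The Grade 2 diarrhea cell, for example, "is recommended to add oral prednisolone 0.5~1 mg/kg (or equivalent) with prolonged taper lasting for at least 4 weeks prednisolone", yet sets no dose for restart. The seventh (adrenal insufficiency and pituitary events, Table 16-3) has its own test, a stable replacement dose with normal hormone levels. If Appendix A displaced 7.3, four steroid-treated holds would have no ceiling at restart.

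**4. The colitis/diarrhea row.** Confirmed Grade 3 or higher colitis ends treatment in both places, so the steroid limit matters only when colitis of that grade is not confirmed.

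- Dose: the row needs strictly less than 10 mg prednisone; 7.3 accepts exactly 10 mg.
- Clock: 7.3 runs out on day 84 after the last dose. With onset d days after that dose, the row runs out on day d + 84. Under on-schedule dosing every 2 weeks, d is at most about 14, giving day 98 at the latest.

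Both are stop rules, and the row contains no permission to restart. A patient at exactly 10 mg at the row's deadline is stopped by the row, and nothing in 7.3 forbids that. A patient above 10 mg through day 84 is stopped by 7.3, and the row's later deadline does not bring the patient back.

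**5. How often.** Table 2-10 (KN046-CHN-001) shows immune-related pneumonitis in 2 of 88 patients, 1 of them Grade 3 or higher, leaving 1 of 88 below Grade 3. Expected among 29: 29 × 1/88 = 0.33. The Clopper-Pearson 95% upper limit for 1/88 is 6.17%, and 29 × 0.0617 = 1.79. At 5 mg/kg every 2 weeks the count is 0/45, with upper limit 7.87% and 29 × 0.0787 = 2.28. The table does not separate Grade 1, where the appendix only suggests considering a delay, so 1/88 may overcount. Every term listed in Table 2-4 (KN046-AUS-001) has at least two subjects, so a single unlisted case cannot be excluded and that trial is left out.

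For the diarrhea row, related Grade 3 or higher diarrhea was 0/142 (0/54 in Table 2-3; absent from Table 2-9, which lists any such event among 88). The upper limit is 2.56%, and 29 × 0.0256 = 0.74.

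**The case against.** The best defense is that the texts already have an order. Section 7.3 is mandatory and covers every drug-related event treated with steroids. Appendix A offers general principles, and its pneumonitis wording is permissive. Someone who applies every limit at once gets one answer: at most 10 mg prednisone. That reading is sensible and safe, but no sentence tells the physician to use it. The pointer in 7.3 leads to a cell that states a restart dose in its own terms. The opposite reading, that the more specific appendix governs, is also available on the page and fails only once the rows with no limit are noticed.

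The size of the gap also depends on a conversion factor that the protocol does not supply, and at a factor of 1 there is none. This stands as a caveat. The mismatch in reference drug does not depend on it.

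A reader might infer more than the documents support:

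- **That the colitis/diarrhea row contradicts 7.3 or grants about 2 extra weeks.** It does not. The two stop rules stack, and the one met first ends treatment.
- **That the pneumonitis row's 12 weeks have no start.** Section 7.3 counts resolution from the last infusion, and Table 7-1 repeats this.
- **That different sites would diverge.** The study is single-center; any divergence is between physicians or between pages.

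**Conclusion.** The point holds as a minor wording error in a safety threshold. Read literally, the Grade 2 pneumonitis row allows a restart at 12 to 12.5 mg/day prednisone equivalent, 2 to 2.5 mg above the 7.3 limit, assuming a factor of 1.2 to 1.25. The colitis/diarrhea row is an untidy mismatch and not a contradiction; its strict inequality is taken as the table reads here.

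On the point estimate, well under one of 29 patients would have a relevant pneumonitis event, and fewer still would be at a dose inside the gap when restart is considered. The upper limits of 1.8 to 2.3 patients reflect sparse data and also come before any dose requirement. Sample size, endpoints and error rates are unaffected.

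**What to change.** 1. In the Grade 2 pneumonitis cell of Table 06-1, replace methylprednisolone 10 mg/day with prednisone 10 mg/day.
2. Add one sentence to section 7.3: its steroid limit and its 12-week clock from the last KN046 dose also apply to immune-related holds managed under Appendix A; physiological hormone replacement (Table 16-3) is exempt; and where Appendix A gives a stricter limit, that limit prevails.
3. Optionally, run the clock in the Grade 3-4 colitis/diarrhea row from the last KN046 dose. Where the rules are already applied together, this changes no decision.

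The cost is one sentence and one or two table cells, with no added patients or procedures. The downside is that a rare pneumonitis patient tapers about 2 mg/day further before restarting. The hormone-replacement exemption is needed because a blanket sentence would otherwise override the separate restart test in Table 16-3.

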#### 7.4. Concurrent medications and therapies

##### 7.4.1 Permitted medications and procedures

Any medications considered necessary for subjects' welfare and will not interfere with KN046 may be given at the investigator's discretion. Other drugs to be used for prophylaxis, treatment of anaphylactic reactions, infusion-related reactions, severe hypersensitivity reaction are described in Sections 7.5.1. The investigator will record all concomitant medications taken by the subject from 28 days prior to first trial treatment, during the study till 90 days after last KN046 dose.

#### **7.4.2 Prohibited medications and procedures**

The following treatments must not be administered during the study:

- Anticancer treatment other than the investigational drug (for example, cytoreductive therapy, radiotherapy, immunotherapies, or cytokine therapy);
- Concurrent systemic therapy with steroids or other immunosuppressive agents with the exception of the treatment of irAEs, prophylactic use to prevent allergic reactions to the contrast for imaging evaluation, for the prevention of acute infusion-related reactions, or administration of steroids for hormone replacement at doses  $\leq 10$  mg or equivalent of prednisone per day. Steroids with no or minimal systemic effect (topical, intranasal, intra-ocular, or inhalation) are allowed;
- Immunosuppressive drugs with the exception for the treatment of irAEs;
- Other investigational drug;
- Major surgery;

If the administration of a nonpermitted concomitant drug becomes necessary during the study, the subject will be withdrawn from treatment with KN046.

#### **7.5. Special precautions**

As a routine precaution, subjects enrolled in this study must be observed for 2 hours after the completion of infusion of KN046 in an area with resuscitation equipment and emergency agents. At all times during study drug administration, immediate emergency treatment of an infusion-related reaction or a severe hypersensitivity reaction according to institutional standards must be assured, for instance, dexamethasone 10 mg and epinephrine in a 1:1000 dilution or equivalents should always be available along with equipment for assisted ventilation.

Infusion of KN046 will be stopped in case of  $\geq$ Grade 3 hypersensitivity or anaphylactic reaction. The treatment recommendations for infusion-related reactions, severe hypersensitivity reactions according to the NCI are outlined in Sections 7.5.1. All infusion-related reactions occurring during the infusion of KN046 or within 2 hours after completion of the administration of KN046 should be reported as AE of interest (See Section 13).

Investigators should monitor subjects closely for potential irAE, which may manifest at the earliest after the first dose of treatment. Such events may consist of autoimmune hepatitis, diarrhea and colitis, arthritis, persistent rash, glomerulonephritis, cardiomyopathy or inflammatory eye conditions etc. Details for irAE management please refer to Section Appendix A.

##### **7.5.1 Infusion-related reactions and hypersensitivity reactions**

Infusion-related reactions could manifest as fever, chills, rigors, diaphoresis or headache. Hypersensitivity reactions could manifest as impaired airway, decreased oxygen saturation ( $<93\%$ ), confusion, lethargy, hypotension, pale or clammy skin and cyanosis.

Management of infusion-related reactions and hypersensitivity caused by KN046 is provided in below

table.

If a hypersensitivity reaction occurs, the subject must be treated according to the best available medical practice. A complete guideline for the emergency treatment of anaphylactic reactions according to the Working Group of the Resuscitation Council (United Kingdom) can be found at <https://www.resus.org.uk/pages/reaction.pdf> (refer to: Emergency Treatment of Anaphylactic Reactions: Guidelines for Healthcare Providers, 2008). Subjects should be instructed to report any delayed reactions to the Investigator immediately.

If severe immediate systemic hypersensitivity occurs, the subject should be placed on a monitor immediately and receive epinephrine and corticosteroid infusion as appropriate. The intensive care unit should be alerted for possible transfer if required.

If the subject is suspected to have systemic hypersensitivity reaction, the investigator is advised to collect plasma histamine, C-reactive protein (CRP) and the presence of drug-specific immunoglobulin E within 30 minutes of system onset, and urinary methyl histamine within 24 hours of onset of symptoms, as well as unplanned ADA and PK samples. For subjects with chest pain, ECG, myocardial enzymes (CPK, CK, Tn1, TnT) and BNP are recommended within 30 minutes of the onset of symptoms.

If investigator determines that the benefit of the continued administration outweighs the risk, the KN046 treatment is allowed to continue and the prophylactic medical must be administered 30-45 minutes prior to the administration of all subsequent dosing cycles. Examples of prophylactic dosing regimens are: diphenhydramine 25~50 mg IV, cimetidine 300 mg IV and acetaminophen 650 mg po.

If the subject's hypersensitivity reaction includes bronchospasm or dyspnea, montelukast 10 mg PO is recommended as part of a prophylactic regimen. Investigators can use medical judgment to determine whether steroids need to be added to a preventive regimen. Encourage discussion with immunologists to determine treatment options.

